7.3 Reporting Procedures – Notifying the IRB

7.3.1 Adverse Event Reporting

Information about observed complications/adverse events will be documented in the electronic data collection system and/or on the paper CRFs, as appropriate. It will be the responsibility of the Principal Investigator to report any Serious Adverse Event (SAE) that occurs during the course of the outcomes data collection to the Institutional Review Board (IRB) within the timeframe specified by NYU SoM.

7.3.2 Unanticipated Problem Reporting

Incidents or events that meet the OHRP criteria for UPs require the creation and completion of an UP report form. It is the site investigator's responsibility to report UPs to their IRB. The UP report will include the following information:

CONFIDENTIAL

This material is the property of the NYU School of Medicine and Langone Medical Center. Do not disclose or use except as authorized in writing by the study sponsor

- Protocol identifying information: protocol title and number, PI's name, and the IRB project number;
- A detailed description of the event, incident, experience, or outcome;
- An explanation of the basis for determining that the event, incident, experience, or outcome represents an UP;
- A description of any changes to the protocol or other corrective actions that have been taken or are proposed in response to the UP.

To satisfy the requirement for prompt reporting, UPs will be reported using the following timeline:

- UPs that are SAEs will be reported to the IRB within 72 hours of the investigator becoming aware of the event.
- Any other UP will be reported to the IRB and to the within 72 hours of the investigator becoming aware of the problem.
- All UPs should be reported to appropriate institutional officials (as required by an institution's written reporting procedures), the supporting agency head (or designee), and OHRP within<insert timeline in accordance with policy> of the IR's receipt of the report of the problem from the investigator.

7.3.3 Reporting of Pregnancy

Pregnant patients will not be included in this study.

7.4 Study Halting Rules

Administration of study agent will be halted when three grade 3 AEs determined to be "probably related" are reported.

7.5 Safety Oversight

It is the responsibility of the Principal Investigator to oversee the safety of the study at his site. The data safety monitoring plan will include careful assessment and appropriate reporting of adverse events as noted above, as well as quarterly review of enrollment, cumulative data from the patient-reported outcomes (pain scores), and adverse events. A yearly summary of adverse events and protocol deviations will be submitted to the IRB with the Continuation Submission in Research Navigator.

8 Clinical Monitoring

Clinical site monitoring is conducted to ensure that the rights and well-being of human subjects are protected, that the reported trial data are accurate, complete, and verifiable, and that the conduct of the trial is in compliance with the currently approved protocol/amendment(s), with GCP, and with applicable regulatory requirement(s).

- Monitoring for this study will be performed by [name].
- The monitoring will be on-site, early, for initial assessment and training, as well as throughout the study. This will be a quarterly review to ensure that:
 - collection and storage of patient data was performed in a sensitive and secure manner, as defined in the informed consent form and protocol
 - All study activities were conducted with primary emphasis on patient care and well-being
 - There were no adverse events
 - The risk/benefit to patients has remained the same throughout the course of the study
- This will be performed on a regular basis (every 3 months)

CONFIDENTIAL

This material is the property of the NYU School of Medicine and Langone Medical Center. Do not disclose or use except as authorized in writing by the study sponsor

9 Statistical Considerations

9.1 Statistical Hypotheses

There is no difference in level of anterior knee pain, as defined by patient-reported functional outcome scores, between the three treatment groups.

9.2 Analysis Datasets

There will be 3 groups for analysis: group 1 will be control, receiving autologous bone graft; group 2 will receive autologous bone graft along with DBM; group 3 will receive autologous bone graft along with calcium phosphate cement. Patients will be randomized to these groups.

9.3 Description of Statistical Methods

9.3.1 General Approach

The general approach of this will be a 3-group study, without crossover. For descriptive statistics, categorical values will be described by percentages, and continuous variables will be described by means with standard deviations. To compare primary and secondary outcomes, an analysis of variance (ANOVA) will be performed, with a p-value of 0.05 set to determine statistical significance. Testing will be performed to determine whether sample distribution is normal; if not, non-parametric testing will be performed.

9.3.2 Analysis of the Primary Efficacy Endpoint(s)

To compare primary outcomes (anterior knee pain), an analysis of variance (ANOVA) will be performed, with a p-value of 0.05 set to determine statistical significance. Testing will be performed to determine whether sample distribution is normal; if not, non-parametric testing will be performed. Patients who do not complete at least 80% of follow-up visits will be considered lost to follow-up and will not be included in the analysis.

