6.1 Study Procedures/Evaluations

6.1.1 Study Specific Procedures

- Medical history (i.e. mechanism of injury, acuity of injury, co-morbidities, smoking status) will be collected by the surgeon during the first office visit
- Physical exam (i.e. height, weight, range of motion, points of pain, ability to bear weight, and assessment of ligamentous laxity) will be performed during the first office visit
- Radiographic images (which may include an X-ray, computed tomography scan, and/or magnetic resonance imaging scan, may be obtain as part of standard of care, independent of this study, to confirm the presence of a torn ACL and search for any concomitant pathology)
- A discussion of if the results of any study specific procedures (e.g., radiographic or other imaging or laboratory evaluations) will be provided to participant.
- If the patient is eligible for the study (i.e. meets inclusion/exclusion criteria), he/she will be informed of the study, and asked if they would like to participate (if yes, consent will be obtained by the surgeon or a study member)
- Once consented, the following questionnaires will be administered: VAS, KOOS, KUJALA IKDC
- On day of surgery, surgeon will ensure patient is aware of their participation in the study, and will consent them for the procedure
- Intraoperatively, when appropriate, the surgeon will use the appropriate graft (autologous bone graft, DBM, or calcium phosphate) based on the group to which the patient was randomized
- The patient will return for post-operative visits at the following intervals: 1 week, 4-6 weeks, 3 months, 6 months, 9 months, and 12 months. During each post-operative visit, the patient will be asked to complete the same survey as completed preoperatively; if unable to obtain during the office visit, patients will be contact via phone within 2 weeks of the visit.

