6.3.4 Final Study Visit

Final Study Visit (12 months \pm 4 weeks)

- Record adverse events as reported by participant or observed by investigator.
- Obtain questionnaire for primary and secondary outcomes (VAS, KOOS, KUJALA IKDC)

CONFIDENTIAL

This material is the property of the NYU School of Medicine and Langone Medical Center. Do not disclose or use except as authorized in writing by the study sponsor

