9.3.3 Analysis of the Secondary Endpoint(s)

To compare secondary outcomes (functional outcomes scores, complication rates), an analysis of variance (ANOVA) will be performed, with a p-value of 0.05 set to determine statistical significance. For categorical variables, chi-squared testing will be performed. Testing will be performed to determine whether sample distribution is normal; if not, non-parametric testing will be performed. Patients who do not complete at least 80% of follow-up visits will be considered lost to follow-up and will not be included in the analysis.

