9.3.4 Adherence and Retention Analyses

Adherence will be defined as patients completing their post-operative visits at the following intervals: 1 week, 4-6 weeks, 3 months, 6 months, 9 months, and 12 months.

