9.4 Sample Size

Based on an effect size of 0.25 with 3 cohorts, a total of 159 patients are needed with 53 in each group. Assuming a 15% drop-out/lost to follow up rate, each group will enroll 60 patients. Outcome measures will include patient reported outcomes: VAS, KOOS, Kujala, and IKDC. Additionally, we will report on rates of complications post-operatively, if any. Type I error rate (alpha) will be set at 0.05. Power will be set at 0.80.

10 Source Documents and Access to Source Data/Documents

Source data is all information, original records of clinical findings, observations, or other activities in a clinical trial necessary for the reconstruction and evaluation of the trial. Source data are contained in source documents. Examples of these original documents, and data records include: hospital records, clinical and office charts, laboratory notes, memoranda, subjects' diaries or evaluation checklists, pharmacy dispensing records, recorded data from automated instruments, copies or transcriptions certified after verification as being accurate and complete, microfiches, photographic negatives, microfilm or magnetic media, x-rays, subject files, and records kept at the pharmacy, at the laboratories, and at medico-technical departments involved in the clinical trial. It is acceptable to use CRFs as source documents. If this is the case, it should be stated in this section what data will be collected on CRFs and what data will be collected from other sources.

The study case report form (CRF) is the primary data collection instrument for the study. All data requested on the CRF must be recorded. All missing data must be explained. If a space on the CRF is left blank because the procedure was not done or the question was not asked, write "N/D". If the item is not applicable to the individual case, write "N/A". All entries should be printed legibly in black ink. If any entry error has been made, to correct such an error, draw a single straight line through the incorrect entry and enter the correct data above it. All such changes must be initialed and dated. DO NOT ERASE OR WHITE OUT ERRORS. For clarification of illegible or uncertain entries, print the clarification above the item, then initial and date it.

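### The 80% attendance rule in Sections 9.3.2 and 9.3.3 drops randomised patients, and their collected scores and complications, from the between-arm comparisons because of what happens after randomisation

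*Combined protocol and SAP*

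**What the plan says.** Section 9.3.2, on the primary endpoint, states that patients who complete fewer than 80% of follow-up visits "will be considered lost to follow-up and will not be included in the analysis". Section 9.3.3 has the same sentence for the secondary outcomes ("Patients who do not complete at least 80% of follow-up visits will be considered lost to follow-up") and names complication rates among the outcomes that it covers.

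Section 9.3.4 lists the follow-up visits: "1 week, 4-6 weeks, 3 months, 6 months, 9 months, and 12 months". That is six visits, in agreement with Sections 6.1.1, 6.3.3 and 6.3.4. The questionnaires are obtained at each one, and so are adverse events ("Record adverse events as reported by participant or observed by investigator", here from Section 6.3.4). Section 6.1.1 provides a fallback for a missed questionnaire: "if unable to obtain during the office visit, patients will be contact via phone within 2 weeks of the visit". It does not say whether a phone questionnaire counts as a completed visit.

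Section 9.2, on analysis datasets, only names the arms ("There will be 3 groups for analysis: group 1 will be control, receiving autologous bone graft", followed by the two other groups). It defines no set of all randomised patients. Nothing from Section 9.2 to Section 9.3.10 gives a missing-data method or a sensitivity analysis. Section 9.4 adds that "we will report on rates of complications post-operatively, if any", without naming a population.

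**The concern.** Who enters the analysis depends on attendance, which is seen only after randomisation and may be affected by pain, recovery or a complication. Selecting on it gives up the protection that randomisation provides.

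The rule also does not track whether the needed outcome exists. A patient who misses weeks 4-6 and month 9 but gives a month-12 pain score is out. A patient who misses only month 12 is in, with no stated method for the missing score. A patient with a patella fracture, a secondary outcome in Section 2.2, leaves the chi-squared comparison after two missed visits.

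The protocol never promises an intention-to-treat analysis, so this is a flawed analysis rule and not an internal contradiction. What is at stake is bias in the pain comparison if attendance relates to outcome differently by arm, an incomplete complication comparison, and some loss of power.

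**Working it through.** **Inputs from the documents.** Six visits (9.3.4); 80% threshold (9.3.2, 9.3.3); effect size 0.25, read as Cohen's f, three groups, 159 evaluable (53 per arm), 60 per arm enrolled (180 in total), 15% loss, alpha 0.05, power 0.80 (4.6, 9.4).

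**Assumptions.** The per-visit miss probability p is not in the documents; 5%, 10% and 15% are used. The plan names no primary time point; month 12 is used.

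**1. The plan's own figure.** ANOVA power from the noncentral F distribution with noncentrality N × 0.25² is 0.805 at N = 159 and 0.797 at 52 per arm. The 159 reproduces.

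**2. Threshold.** 0.80 × 6 = 4.8. Five of six (83.3%) stays in; four of six (66.7%) is out.

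**3. Independent misses, q = 1 − p.**
- Retained: q⁶ + 6pq⁵
- Excluded despite a month-12 score: q(1 − q⁵ − 5pq⁴)
- Month-12 scores analysed with the rule: 180q(q⁵ + 5pq⁴); without it: 180q

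| | p = 5% | p = 10% | p = 15% |
|---|---|---|---|
| Excluded | 3.3% | 11.4% | 22.4% |
| Retained of 180 | 174 | 159 | 140 |
| Power if every retained patient can be analysed | 0.84 | 0.805 | 0.748 |
| Excluded with a month-12 score | 2.1% (about 4) | 7.3% (about 13) | 14.0% (about 25) |
| Month-12 n with the rule (power) | 167 (0.83) | 149 (0.78) | 128 (0.71) |
| Month-12 n without the rule (power) | 171 (0.83) | 162 (0.81) | 153 (0.79) |

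Under independence, exclusions reach the planned 15% at p = 11.7%.

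**4. Clustered misses (beta-binomial).** At p = 15%, month-12 scores discarded fall from 14.0% to 9.9% (ICC 0.4) or 6.6% (ICC 0.6). At p = 5% they rise, from 2.1% to 3.5% at ICC 0.4. At p = 10% and ICC 0.4, total exclusions are 15.1%, leaving about 153 patients and power 0.788. The 15% allowance is then used up at about p = 10%.

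**5. Pure dropout.** No month-12 score is discarded, because nobody who has one has missed a visit. A patient who stops after month 6 has four of six visits and still loses four visits' worth of scores.

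**6. Bias.** Suppose one arm excludes a fraction d, with correlation ρ between pain and exclusion, and the other arms lose patients at random. The arm mean shifts by ρφ(z)/(1 − d) SD, where z is the standard normal quantile at 1 − d. φ(z) is 0.1755 at d = 10% and 0.2332 at d = 15%. The false-positive rate is the ANOVA rejection rate with 53 per arm and noncentrality 53 × shift² × 2/3.

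| ρ | d | Shift (SD) | False-positive rate |
|---|---|---|---|
| 0.3 | 10% | 0.059 | 5.9% |
| 0.3 | 15% | 0.082 | 6.8% |
| 0.5 | 10% | 0.098 | 7.6% |
| 0.5 | 15% | 0.137 | 10.2% |

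A simulation with 60 per arm enrolled (8,000 runs each) gave 5.9%, 7.4%, 7.5% and 10.1%. Setting ρ = 1 gives 0.195 and 0.274 SD. That is an upper bound, since the arm would have to lose exactly its worst-pain 10% to 15%. If the mechanism and the exclusion rate are the same in all arms, the shift cancels.

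For scale: if f = 0.25 comes from one arm differing from two equal arms, the design difference is 0.25 × 3/√2 = 0.53 SD. A shift of 0.059 to 0.137 SD is about 11% to 26% of that.

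**The case against.** The strongest case is that the practical harm may be small and cannot be sized from the documents. Visits follow the standard-of-care schedule, the later windows are ±4 weeks, and missed questionnaires are pursued by phone; if those count as visits, few patients may be excluded. Section 9.4 already budgets 15% for loss, and at p = 10% with independent misses the 0.80 target is still met when every retained patient can be analysed. At p = 15%, month-12 power is below 0.80 even without the rule. The bias needs an arm-specific link between pain and attendance, for which there is no evidence.

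It can also be said that the data are not lost to the study. Section 7.5 provides quarterly review of pain scores and adverse events and a yearly summary to the IRB, Section 9.3.9 has individual data recorded, and Section 9.4 promises complication rates without an 80% limit.

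Much of this stands as limits on size. Power alone would not make this a serious point, and the loss is from the comparative analyses, not from the record. But none of these provisions returns a patient to the between-arm tests, and the 15% allowance deals with sample size, not selection. The phone route would narrow the rule without removing it. A plan should not rest on attendance being unrelated to outcome, or related equally in every arm, when the excluded data are already in hand.

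**Conclusion.** The concern holds, and the rule must be fixed before the analysis. That the rule removes anyone below five of six visits from both the primary and secondary comparisons, complication rates included, follows directly from the text and needs no assumption.

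Its size does need assumptions. For per-visit miss rates of 5% to 15%, independent across visits, 3.3% to 22.4% of patients are excluded, and 2.1% to 14.0% of all randomised lose an available month-12 score. Month-12 power falls by roughly 0.01, 0.04 and 0.08 at the three rates; at 10% the rule takes it below the 0.80 target, which is met without the rule. Clustering and dropout patterns change these figures as shown. The false-positive rate of about 6% to 10% depends on the assumed one-arm mechanism. The documents do not show that attendance will differ by arm.

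**What to change.** 1. Delete the 80% sentence from Sections 9.3.2 and 9.3.3.
2. In Section 9.2, define the primary analysis set as all randomised patients, in their assigned arm, with all available scores. A repeated-measures mixed model for the continuous scores, with the contrast at a prespecified visit, is one suitable option. It requires the plan to name the primary instrument and visit.
3. Include all randomised patients in the complication-rate comparison.
4. Because a mixed model assumes data missing at random, add a sensitivity analysis for departures from that, such as delta-adjusted multiple imputation by arm.
5. Keep the five-of-six completer analysis as supportive only, and state whether a phone questionnaire counts as a completed visit for it.

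The cost is a change to Section 9, which as protocol text needs IRB approval under Section 12.2, and slightly more analysis work. No extra patients or visits are needed, since the scores and adverse events are already collected.

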9.3.3 Analysis of the Secondary Endpoint(s)

To compare secondary outcomes (functional outcomes scores, complication rates), an analysis of variance (ANOVA) will be performed, with a p-value of 0.05 set to determine statistical significance. For categorical variables, chi-squared testing will be performed. Testing will be performed to determine whether sample distribution is normal; if not, non-parametric testing will be performed. Patients who do not complete at least 80% of follow-up visits will be considered lost to follow-up and will not be included in the analysis.

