2.2 Secondary Objectives (if applicable)

Secondary outcomes include patient reported quality of life and functional outcome measures, rate (if any) of patella fracture, rate of return to activity, cost effectiveness and adverse events.

3 Study Design and Endpoints

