9.3.8 Multiple Comparison/Multiplicity

Not applicable.

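### Section 9.3.3 lets each secondary outcome be called significant at its own 0.05 whatever the pain result, with no multiplicity rule; for three scores at one visit the chance of a false claim is about 0.085 to 0.14

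*Combined protocol and SAP*

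**What the plan says.** Section 9.3.1 applies one rule to both tiers: "To compare primary and secondary outcomes, an analysis of variance (ANOVA) will be performed, with a p-value of 0.05 set to determine statistical significance". Section 9.3.3 repeats it for the secondary outcomes in a sentence that begins "To compare secondary outcomes (functional outcomes scores, complication rates), an analysis of variance (ANOVA) will be performed, with a p-value of 0.05 set to determine", and the functional scores and complication rates are the only outcomes it names. For counts and rates the section also says "For categorical variables, chi-squared testing will be performed". Section 9.3.8 on multiplicity says only "Not applicable", and 9.3.10 makes the same entry for exploratory analyses, so no outcome is set aside as exploratory. Section 9.4 states "Type I error rate (alpha) will be set at 0.05" as part of the sample-size basis.

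The list of secondary outcomes is not settled:

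- Section 2.2: "Secondary outcomes include patient reported quality of life and functional outcome measures, rate (if any) of patella fracture, rate of return to activity, cost effectiveness", followed by adverse events.
- Section 3.2.1 puts KOOS, Kujala, IKDC and VAS pain together under the primary endpoint.
- Section 3.2.2 says that there are no further secondary endpoints.
- Section 9.1 defines anterior knee pain through the patient-reported functional scores.
- Section 9.3.2 takes anterior knee pain as primary, and 9.3.3 takes the functional scores as secondary.

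The questionnaires are collected at six postoperative visits (6.1.1, 6.3.3, 6.3.4). Section 9.3.3 names no visit for analysis.

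**The concern.** If the pain comparison is null, the plan still allows a functional score or a complication rate with p<0.05 to be reported as statistically significant. With several such tests, the chance that at least one is falsely significant exceeds 0.05. Section 1.1 says that surgeons at this institution do not agree on the filler material, so an isolated secondary result could be taken as the trial's answer. Section 9.3.8 is where a rule would be expected. Multiplicity does apply here, because 9.3.3 itself provides for more than one secondary test.

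**Working it through.** **1. The plan's own figure.** Inputs from 9.4: effect size 0.25 (read as Cohen's f), 3 groups, alpha 0.05, power 0.80. For a one-way ANOVA the noncentrality is N × f². With N = 159 this is 159 × 0.0625 = 9.94, on 2 and 156 degrees of freedom, with critical F = 3.054. Power is 0.805; at N = 156 it is 0.797. The stated 159 (53 per group) therefore reproduces as the size for one F test. The 0.05 in 9.4 is the error rate of that single test.

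**2. Independent tests, as a reference.** With k tests at 0.05 and all nulls true, P(at least one p<0.05) = 1 − 0.95^k.

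- k = 1: 0.05
- k = 3: 1 − 0.857 = 0.143 (2.85 times 0.05)
- k = 7: 1 − 0.698 = 0.302 (6.0 times 0.05)

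**3. Correlated scores.** The three scores come from the same patients, so independence overstates the rate. I simulated three-group ANOVAs with 53 per group, normal outcomes with one common correlation, and no true differences. KOOS, Kujala and IKDC count as one score each. There were 40,000 null trials for 3 tests and 10,000 for 18 tests (3 scores × 6 visits). The documents give no correlations, so a range is shown.

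| Assumed correlation | 3 scores, one visit | Ratio to 0.05 | 3 scores, six visits | Ratio to 0.05 |
|---|---|---|---|---|
| 0.3 | 0.139 | 2.8 | 0.511 | 10.2 |
| 0.5 | 0.128 | 2.6 | 0.407 | 8.1 |
| 0.7 | 0.113 | 2.3 | 0.284 | 5.7 |
| 0.9 | 0.086 | 1.7 | 0.161 | 3.2 |

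With separate correlations between scores (0.3 to 0.9) and between visits (0.3 to 0.7), the six-visit figure is about 0.27 to 0.55.

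**4. Adding a complication test.** The true size of a 3 × 2 chi-squared test with 53 per arm, computed exactly, is about 0.017 at a 1% event rate and 0.004 at 0.5%. It comes near 0.05 only for commoner events (0.046 at 10%). Start from 0.128 and assume that the added test is independent:

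- 1% event rate: 1 − 0.872 × 0.983 = 0.143
- 0.5% event rate: 1 − 0.872 × 0.996 = 0.131
- full 0.05 size: 1 − 0.872 × 0.95 = 0.172

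A rare outcome such as patella fracture therefore adds little.

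**5. More outcomes at one visit.** The three scores plus patella fracture, return to activity, cost effectiveness and adverse events make seven. The rate would run from 0.119 (all correlated at 0.9) to 0.302 (independent). The upper end is generous if some of the seven are rare events.

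**The case against.** The strongest reply is that nothing stated is breached. The 0.05 is a per-test threshold, each test keeps that rate, and no familywise rate is promised for secondary outcomes. Unadjusted secondary analyses are also common. The first part stands. The second would answer the point if the plan called these results supportive, but it instead sets a threshold for declaring them significant.

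Some stronger readings are tempting, but the documents do not support them:

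- **A fixed multiplier.** A reader might infer that a false secondary claim is 2.6 to 8 times as likely as 0.05. Those are two scenarios (3 and 18 tests) at one assumed correlation of 0.5, and they are neither lower nor upper bounds. The larger needs a test at every visit, which 9.3.3 neither requires nor rules out. The visit schedule governs data collection and does not prescribe significance tests.
- **Equal standing with the primary.** Sections 9.3.2 and 9.3.3 separate the tiers, and the only hypothesis in 9.1 concerns anterior knee pain. The threshold and the word significance are shared, but that does not give the tiers equal rank.
- **A named filler shown to be better.** The simulated event is a significant overall test. Section 9.3.3 specifies no pairwise comparisons, so that event alone does not single out one filler.

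A further objection is that 3.2.1 makes these scores primary. If that section governs, the three tests above belong to the primary endpoint and the multiplicity arises there. The calculation applies to the secondary tier only if 9.3.3 governs, or if one primary measure is chosen and the other scores become secondary. This also stands, and it makes the reconciliation a first step.

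**Conclusion.** The point holds in a limited form. As written, any secondary outcome can be declared significant at p<0.05 whatever the pain result, and the plan has no multiplicity rule. For KOOS, Kujala and IKDC at one visit, the chance of at least one false declaration is about 0.085 to 0.14 when nothing differs. It is about 0.16 to 0.51 if all six visits are tested under one common correlation, which the plan leaves open. These figures assume 53 evaluable patients per arm, normal outcomes, one score per instrument, correlations of 0.3 to 0.9, and that these three scores are secondary. An exact multiplier cannot be given until the secondary outcomes and the visit are fixed. The direction does not depend on the assumed values: even the most favourable case shown is about 1.7 times 0.05. The change should be made, but this point does not undermine the primary test or its sample size.

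**What to change.** First reconcile 2.2, 3.2.1, 3.2.2, 9.1 and 9.3.3, so that it is clear which scores are primary and which are secondary. Then:

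1. In 9.3.3, replace the significance sentence with a statement that secondary outcomes are supportive, are reported as between-group differences with 95% confidence intervals, and carry no claim of statistical significance.
2. Also in 9.3.3, report complication and patella-fracture rates as counts, rates and confidence intervals by arm, without a significance threshold.
3. In 9.3.8, replace the present entry with the same rule.
4. If the sponsor wants confirmatory secondary claims, test them only after a significant primary pain test, at one named visit, in a prespecified order or with Holm. For three scores, Holm's first step is 0.05 / 3 = 0.0167; for independent tests this gives 1 − (1 − 0.0167)³ = 0.049. The visit, and the order if one is used, must be named before the data are seen.

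The cost is wording plus the decision on which scores are secondary. No extra patients or data are needed, and the primary test keeps its 0.05, so the sample-size basis is unchanged. The downside is that an isolated secondary p<0.05 can no longer be called significant when the primary test fails.

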1.2.1 Known Potential Risks

The differing materials used will not prolong or significantly extend the time of surgery.

Possible adverse effects of using DBM include, but are not limited to: infection of soft tissue or bone, fever, deformity of the bone at the site of use, incomplete bone ingrowth, fracture of newly formed bone, hypercalcemia or transient hypercalcemia.

Possible adverse effects of using calcium phosphate cement include, but are not limited to: wound infection, wound dehiscence, fracture, loss of reduction, delayed or non-consolidation. While these risks are rare we will continue to monitor your condition to make sure these risks are minimized.

However, use of these elements are all considered standard of practice and used by surgeons at this institution and therefore, will not increase the level of risk for the patient beyond the normal surgery.

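### Section 9.3.3 gives complication rates two methods (ANOVA and chi-squared) and no rule for sparse tables, so p-values near 0.05 for rare events such as patella fracture would be unreliable (minor)

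*Combined protocol and SAP*

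**What the plan says.** Section 9.3.3 (Analysis of the Secondary Endpoint(s)) opens with "To compare secondary outcomes (functional outcomes scores, complication rates), an analysis of variance (ANOVA) will be performed", at a 0.05 threshold. It continues: "For categorical variables, chi-squared testing will be performed". Its only fallback is "Testing will be performed to determine whether sample distribution is normal; if not, non-parametric testing will be performed". Neither this section nor the general approach in Section 9.3.1 names an exact test or a minimum expected count.

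Section 2.2 lists the "rate (if any) of patella fracture" among the secondary outcomes. Section 9.4 says "we will report on rates of complications post-operatively, if any". Section 1.2.1 adds "While these risks are rare" after a list of possible effects of calcium phosphate cement, fracture among them. No complication rate is given anywhere.

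The denominators come from Section 9.4: "Based on an effect size of 0.25 with 3 cohorts, a total of 159 patients are needed with 53 in each group", with 60 per group enrolled. Section 3.1 specifies simple randomization, so arms of equal size are planned but not guaranteed.

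**The concern.** There are two gaps. First, a complication is a yes/no event per patient, yet the section assigns it to ANOVA in one sentence and, as a categorical variable, to chi-squared in the next. Second, the Pearson chi-squared p-value relies on a large-sample approximation that is doubtful when expected counts are small, and here they probably will be. The non-parametric fallback does not help, because a normality check concerns continuous scores and not sparse event counts.

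At stake is a safety statement. If one filler had a few fractures and the others none, the plan's test could put the difference just under 0.05 while an exact test would not. With no rule fixed in advance, the analyst would also be choosing between two p-values after seeing the data.

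**Working it through.** **Inputs.** 53 evaluable per arm, 159 in total, three arms (Section 9.4); threshold 0.05 (Section 9.3.3); simple randomization (Section 3.1). The documents give no event rate, so true rates of 0.5% to 5% are assumed where a rate is needed.

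**The plan's own figure.** One-way ANOVA with effect size f = 0.25, three groups, alpha 0.05 and power 0.80 needs N = 157.2. Rounded up to equal groups this is 53 × 3 = 159, with power 0.805. The 159 reproduces.

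**When expected counts are small.** With T events in total and equal arms, the expected count per arm is T × 53/159 = T/3. It reaches 5 only at T = 15. The chance of fewer than 15 events in 159 patients is above 99.9% at rates of 0.5% to 3%, and 98.6% at 5%.

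**Split 3-0-0, 53 per arm.** The expected count is 1 per arm.
- Pearson: X² = [(3−1)² + (0−1)² + (0−1)²] / [1 × (1 − 3/159)] = 6/0.9811 = 6.115. On 2 df, p = exp(−6.115/2) = 0.047.
- Fisher-Freeman-Halton: no split of three events is less probable than all three in one arm, so p = 3 × C(53,3)/C(159,3) = 3 × 23,426/657,359 = 0.107.
- ANOVA on the 0/1 data also gives p = 0.047, so the section's other method does not remove the discrepancy.
- At 60 per arm the values are 0.0473 and 0.1074.

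**Split 6-1-1, 53 per arm.** The expected count is 8/3 = 2.667. X² = [(3.333)² + 2 × (1.667)²] / [2.667 × (1 − 8/159)] = 16.667/2.5325 = 6.581, so p = exp(−6.581/2) = 0.037. The exact p is 0.051.

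**Other splits at 53 per arm.**

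| Split | Chi-squared p | Exact p |
|---|---|---|
| 3-1-0 | 0.166 | 0.325 |
| 4-0-0 | 0.0165 | 0.034 |
| 5-1-0 | 0.026 | 0.048 |

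In these three the p-values differ but fall on the same side of 0.05.

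**Error rate given three events.** At exactly equal arms, only 3-0-0 and its permutations reject by chi-squared, so the conditional rejection rate under the null is 10.7%. Simple randomization produces exactly equal arms in only about 0.5% of allocations. Averaged over allocations, the rate given three events is about 4.5%. It exceeds 5% in about 55% of allocations and is lower in the rest.

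**Error rate over all totals.** At equal arms, chi-squared rejects a true null between 0.4% (rate 0.5%, 53 per arm) and 4.3% (rate 5%, 60 per arm) of the time. Under simple randomization with N = 159:

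| True rate | Chi-squared | Exact |
|---|---|---|
| 1% | 1.0% | 0.6% |
| 2% | 2.5% | 2.1% |

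**How often 3-0-0 arises at equal arms.** Exactly three events in 159 has probability 13.7% at a 1% rate and 22.5% at 2%. Multiplied by 0.107, all three falling in one arm under the null has probability 1.5% to 2.4%.

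**The case against.** The strongest reply is that chi-squared does no harm on average: its overall type I error stays below 5% at every rate examined. That stands. A reader might infer from 3-0-0 that the plan doubles the false-positive rate for safety outcomes. The documents do not support this, because the 10.7% needs exactly equal arms and Section 3.1 does not provide for them.

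The example also sits on a knife edge. With arms of 61/60/59 and all three events in the arm of 61, chi-squared gives 0.051 and the exact test 0.107. With 58/61/61 and all three in the arm of 58, chi-squared gives 0.040 and the exact test 0.032. So it cannot be said that three fractures in one arm would always be significant by one test and not by the other, and the example requires no events in the other two arms. Nor is 3-0-0 a likely table.

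The evidence of rarity is indirect. The remark in Section 1.2.1 concerns cement effects and not patella fracture, and a pooled complication rate might have adequate counts. This stands as a caution. A rule triggered by the expected count deals with it, since chi-squared is kept when counts suffice.

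Finally, the exact test is more conservative, which matters when looking for harm. At exactly equal arms its overall size is 0.2% at a 1% rate and 1.1% at 2%, against 1.7% and 3.5% for chi-squared. Under simple randomization the loss is small (0.6% against 1.0%, and 2.1% against 2.5%). Switching tests at analysis is routine, but an unplanned switch leaves the choice open once the data are known.

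**Conclusion.** The point holds as a minor one. Section 9.3.3 names two methods for one outcome and has no sparse-table rule, and at the planned equal arms the choice of test moves 3-0-0 (0.047 against 0.107) and 6-1-1 (0.037 against 0.051) across 0.05. The problem is confined to tables near the threshold. It is not a general inflation of type I error, and the primary comparison and the sample size are unaffected.

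The two p-value comparisons need no assumed event rate, only the stated splits and equal arms. The statements about how often sparse tables arise rest on assumed rates of 0.5% to 5%. The exact test is preferred because it holds the conditional level whatever the allocation, at little cost.

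**What to change.** In Section 9.3.3:
- Remove complication rates from the ANOVA sentence, leaving the functional scores there.
- State that complication rates, including patella fracture, are compared across the three arms by chi-squared, or by the Fisher-Freeman-Halton exact test whenever any expected count is below 5.
- State that each arm's rate is reported with an exact 95% confidence interval. This stays informative with no events: for 0 of 53 the upper limit is 1 − 0.025^(1/53) = 6.7%.

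The edit takes a few sentences and needs no extra patients, visits or data. The statistical cost is a somewhat more conservative test at very low event totals; at exactly equal arms it cannot reject with three events. The intervals should therefore be read alongside the p-value.
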